1.1 Background

1.1.1 Cardiovascular benefits of lowering LDL cholesterol

Elevated low-density lipoprotein associated cholesterol (LDL-C), is one of the major risk factors for coronary heart disease (CHD) (Grundy et al, 2004). Despite advances in treatment, atherosclerotic cardiovascular disease (ASCVD) is the leading cause of death and disability worldwide and is expected to remain so beyond 2040 (Foreman et al, 2018). After 30 years of progress, death rates associated with ASCVD may be increasing in the United States once more (Benjamin et al, 2019).

Multiple factors contribute to the development of ASCVD. However, strong and consistent evidence from genetics, epidemiology, and randomised trials, establishes that among these factors, LDL-C is not merely a biomarker of increased risk, but a causal and modifiable factor in ASCVD (Ference et al, 2017).

Large outcome trials have consistently confirmed the benefit of cholesterol lowering therapy (statins). In the largest study, the Heart Protection Study, 20,536 subjects were treated with simvastatin for five years. The study was large enough to allow multiple subgroup analyses. These showed that the reduction in relative risk was similar even when subjects had risk factors including diabetes, hypertension, and smoking (Goldstein, 2015). A recent meta-analysis of 22 statin trials involving 134,000 participants concluded that for each reduction of LDL-C of 1 mmol/l (40 mg/dl) cardiovascular events are reduced by 20%, even in people who were considered to be at low risk (Cholesterol Treatment Trialists, 2012). These findings have made statin the cornerstone of clinical practice.

Despite the proven efficacy of statins, there is still a considerable variability in individuals to these drugs, even when being treated with a high intensity regime (Ridker, 2016). Furthermore, not all people tolerate statins or are able to take statins at sufficient intensive doses, and some observational studies have demonstrated as many as half of individuals who begin statin therapy discontinue it within 12 months (Zang, 2013).

Therefore, there is a clear unmet medical need for additional options beyond current available treatments for the lowering of LDL-C.

1.1.2 Inhibition of PCSK9 as a therapeutic target

LDL Receptors (LDLR) on the surface of liver cells are a key determinant of circulating levels of LDL-C (Goldstein and Brown, 2009). Proprotein convertase subtilisin/kexin type 9 (PCSK9) is an enzyme mainly of hepatic origin that circulates in the blood and binds to the LDLR (Seidah, 2014). The PCSK9-LDLR complex is then degraded by lysosomes in the liver cells and circulation of LDLR to the surface of the liver cells is reduced. As a consequence, the number of LDL receptors on liver cells is reduced and there is reduced uptake of LDL-C from the blood (Horton et al, 2007). Lower levels of circulating PCSK9 lead to higher hepatic LDLR expression and lower circulating LDL-C levels.

Gain of function mutations in the PCSK9 gene result in familial hypercholesterolaemia and increased rates of coronary events. By contrast, loss of function mutations are associated with

Novartis	Confidential	Page 24 of 85
CLINICAL TRIAL PROTOCOL: Version 02	Protocol No. CKJX839A1GB	01 (VICTORION Spirit)

reductions in LDL-C levels and lower risk of coronary events. From a safety perspective, individuals with no circulating PCSK9 due to compound heterozygous loss of function mutations in PCSK9 do not appear to have any obvious clinical disadvantages (Zhao, 2006). Mechanistic studies of PCSK9 have identified PCSK9 as playing a key role in controlling the levels of LDLR on the surface of hepatocytes. PCSK9 is responsible for degrading LDLR and prevents recycling to the cell surface where it removes LDL-C from the plasma. Therapeutic strategies designed to reduce circulating PCSK9 include binding it in the circulation with monoclonal antibodies or modified binding proteins and reducing production of it in the liver with small interfering RNAs (siRNAs).

Clinical studies with PCSK9 blocking antibodies have demonstrated significant effects on lowering LDL-C in healthy volunteers and in subjects with hypercholesterolemia with and without statins (Banerjee, 2012, Dias et al, 2012, Milazzo, 2012, Raal et al 2012). In addition, recent clinical studies indicate that statin treatment increases PCSK9 levels and as a result, may limit statin effectiveness as the dose is increased (Careskey et al, 2008; Davignon and Dubuc, 2009; Welder et al, 2010). Collectively these studies support the hypothesis that lowering of circulating plasma PCSK9 by inhibiting the synthesis of PCSK9 protein in hepatocytes should lower LDL-C, potentially resulting in reduced risk of CHD.

1.1.3 Inhibition of PCSK9 with siRNA has potential advantages over antibodies

Ribonucleic acid interference (RNAi) is a naturally occurring cellular mechanism mediated by small interfering RNAs (siRNAs) for regulating gene expression. Inclisiran is a chemically synthesised siRNA, covalently linked to a ligand containing three N-acetylgalactosamine (GalNAc) residues. These GalNAc residues bind to abundant liver-expressed asialoglycoprotein receptor (ASGPR), leading to inclisiran uptake specifically into hepatocytes. When introduced into the hepatocyte, inclisiran engages the natural pathway of RNA interference (RNAi) by binding intracellularly to the RNA-induced silencing complex (RISC), enabling it to cleave mRNA molecules encoding PCSK9 specifically. The cleaved PCSK9 mRNA is degraded and thus unavailable for protein translation, which results in decreased levels of the PCSK9 protein. A single siRNA-bound RISC is catalytic and cleaves many mRNA transcripts and the duration of action is anticipated to be longer than other mechanisms. A key potential advantage of inclisiran's mechanism of action is that the duration of its effect is longer than that of monoclonal antibodies to PCSK9.

1.1.4 Clinical efficacy and safety

The efficacy of inclisiran was evaluated in three phase III studies in patients with ASCVD or ASCVD risk equivalents (type 2 diabetes mellitus, familial hypercholesterolaemia, or 10-year risk of 20% or greater of having a cardiovascular event assessed by Framingham Risk Score or equivalent) and/or familial hypercholesterolaemia (FH). Patients were taking a maximally tolerated dose of statin with or without other lipid-modifying therapy and required additional LDL-C reduction (patients unable to reach their treatment goals). Approximately 17% of patients were statin intolerant. Patients were administered subcutaneous injections of 284 mg inclisiran or placebo on day 1, day 90, day 270 and day 450. Patients were followed until day

540. The effect of inclisiran on cardiovascular morbidity and mortality has not yet been determined.

In the phase III pooled analysis, subcutaneously administered inclisiran lowered LDL-C between 50% and 55% as early as day 90 (Figure 1-1), which was maintained during long-term therapy. Maximal LDL-C reduction was achieved at day 150 following a second administration. Small but statistically significant increased LDL-C reductions up to 65% were associated with lower baseline LDL-C levels (approximately <2 mmol/l [77 mg/dl]), higher baseline PCSK9 levels and higher statin doses and statin intensity.

Figure 1-1 Mean percentage change from baseline LDL-C in patients with primary hypercholesterolaemia and mixed dyslipidaemia treated with inclisiran compared to placebo (pooled analysis)

To date, injection site reaction is the only adverse drug reaction that has been identified for inclisiran. None of the reported injection site reactions were considered to be serious.

In Phase II study MDCO-PCS-15-01 (ORION-1), clinically relevant injection site reactions were reported in a total of 13 (3.5%) inclisiran-treated subjects and no subjects (0.0%) in the placebo group following a single dose (single and double dose groups combined) through Day 90. Injection site reactions were reported in a total of 6 (3.4%) inclisiran-treated subjects and no subjects (0.0%) in the placebo group following a second dose. No observed difference or dose relationship was observed between inclisiran groups. The frequency of injection site reactions was similar after a second dose of inclisiran (3.4%) to that observed after the first dose (3.5%). All AEs at the injection site resolved without sequelae with the exception of one subject who received a single dose of inclisiran sodium 300 mg on Day 1 and continued to have a 2 mm erythema spot at the injection site on Day 210.

Novartis	Confidential	Page 26 of 85
CLINICAL TRIAL PROTOCOL: Version 02	Protocol No. CKJX839A1GE	301 (VICTORION Spirit)

In the Phase III studies MDCO-PCS-17-03 (ORION-9), MDCO-PCS-17-04 (ORION-10) and MDCO-PCS-17-08 (ORION-11), more inclisiran-treated subjects, 8.2% (150/1833), reported at least one Treatment Emerged Adverse Events (TEAE) at the injection site than placebo-treated subjects 1.8% (33/1822). Of the 183 subjects with a TEAEs at the injection site, the majority had a mild event (4.2%; 154/3655 subjects) and none had a severe event. No inclisiran-treated subject had a serious TEAE at the injection site. Four (4) inclisiran-treated subjects withdrew from study drug due to non-serious TEAEs at the injection site.

From the reported TEAEs at the injection site, more inclisiran-treated subjects (5.0%; 91/1833) reported clinically relevant TEAEs at the injection site (preferred terms of injection site erythema, injection site hypersensitivity, injection site pruritus, injection site rash, and injection site reaction) than placebo-treated subjects (0.7%; 12/1822). Clinically relevant TEAEs at the injection site were reported for inclisiran-treated subjects as follows: injection site erythema (37 events in 30 subjects), injection site hypersensitivity (3 event in 2 subjects), injection site pruritus (9 events in 8 subjects), injection site rash (20 events in 13 subjects), and injection site reaction (84 events in 56 subjects). The time to first clinically relevant TEAEs at the injection site was usually observed more than 12 hours after the time of injection and this was similar for those that were clinically relevant. The TEAE at the injection site were generally transient.

1.1.4.1 ASCVD and ASCVD risk equivalents

Two studies were conducted in patients with ASCVD and ASCVD risk equivalents (ORION-10 and ORION-11). Patients were taking a maximally tolerated dose of statins with or without other lipid-modifying therapy, such as ezetimibe, and required additional LDL-C reduction. As lowering LDL-C is expected to improve cardiovascular outcomes, the co-primary endpoints in each study were the percentage change in LDL-C from baseline to day 510 relative to placebo and the time-adjusted percentage change in LDL-C from baseline after day 90 and up to day 540 to estimate the integrated effect on LDL-C over time.

ORION-10 was a multicentre, double-blind, randomised, placebo-controlled 18-month study conducted in 1,561 patients with ASCVD. The mean age at baseline was 66 years (range: 35 to 90 years), 60% were \geq 65 years old, 31% were women, 86% were White, 13% were Black, 1% were Asian and 14% were Hispanic or Latino ethnicity. The mean baseline LDL C was 2.7 mmol/1 (105 mg/dl). Sixty-nine percent (69%) were taking high-intensity statins, 19% were taking medium-intensity statins, 1% were taking low-intensity statins and 11% were not on a statin. The most commonly administered statins were atorvastatin and rosuvastatin.

Inclisiran significantly reduced the mean percentage change in LDL-C from baseline to day 510 compared to placebo by 52% (95% CI: -56%, -49%; p <0.0001).Inclisiran also significantly reduced the time-adjusted percentage change in LDL-C from baseline after day 90 and up to day 540 by 54% compared to placebo (95% CI: -56%, -51%; p <0.0001). At day 510, the LDL-C target of <1.8 mmol/l (70 mg/dl) was achieved by 84% of inclisiran patients with ASCVD compared to 18% of placebo patients.

Consistent and statistically significant (p<0.0001) reductions in percentage change in LDL-C from baseline to day 510 and time-adjusted percentage change in LDL-C from baseline after day 90 and up to day 540 were observed across all subgroups irrespective of baseline

demographics, baseline disease characteristics (including gender, age, body mass index, race and baseline statin use), comorbidities and geographic regions.

ORION-11 was an international, multicentre, double-blind, randomised, placebo-controlled 18-month study which evaluated 1,617 patients with ASCVD or ASCVD risk equivalents. More than 75% of patients were receiving a high-intensity statin background treatment, 87% of patients had ASCVD and 13% were ASCVD risk equivalent. The mean age at baseline was 65 years (range: 20 to 88 years), 55% were \geq 65 years old, 28% were women, 98% were White, 1% were Black ,1% were Asian and 1% were Hispanic or Latino ethnicity. The mean baseline LDL-C was 2.7 mmol/l (105 mg/dl). Seventy-eight percent (78%) were taking high-intensity statins and 5% were not on a statin. The most commonly administered statins were atorvastatin and rosuvastatin.

Inclisiran significantly reduced the mean percentage change in LDL-C from baseline to day 510 compared to placebo by 50% (95% CI: -53%, -47%; p<0.0001). Inclisiran also significantly reduced time-adjusted percentage change in LDL-C from baseline after day 90 and up to day 540 by 49% compared to placebo (95% CI: -52%, -48%; p<0.0001).

At day 510, the LDL-C target of <1.8 mmol/l (70 mg/dl) was achieved by 82% of inclisiran patients with ASCVD compared to 16% of placebo patients. In patients with an ASCVD risk equivalent, the LDL-C target of <2.6 mmol/l (100 mg/dl) was achieved by 78% of inclisiran patients compared to 31% of placebo patients.

Consistent and statistically significant (p<0.05) percentage change in LDL-C from baseline to day 510 and time-adjusted percentage change in LDL-C from baseline after day 90 and up to day 540 was observed across all subgroups irrespective of baseline demographics, baseline disease characteristics (including gender, age, body mass index, race and baseline statin use), comorbidities, and geographic regions.

1.1.4.2 Heterozygous familial hypercholesterolaemia

ORION-9 was an international, multicentre, double-blind, randomised, placebo-controlled 18-month trial in 482 patients with heterozygous familial hypercholesterolaemia (HeFH). All patients were taking maximally tolerated doses of statins with or without other lipid-modifying therapy, such as ezetimibe, and required additional LDL-C reduction. The diagnosis of HeFH was made either by genotyping or clinical criteria ("definite FH" using either the Simon Broome or WHO/Dutch Lipid Network criteria).

The co-primary endpoints were the percentage change in LDL-C from baseline to day 510 relative to placebo, and the time-adjusted percentage change in LDL-C from baseline after day 90 and up to day 540 to estimate the integrated effect on LDL-C over time. Key secondary endpoints were the absolute change in LDL-C from baseline to day 510, the time-adjusted absolute change in LDL-C from baseline after day 90 and up to day 540 and the percentage change from baseline to day 510 in PCSK9, total cholesterol, Apo-B, and non-HDL-C. Additional secondary endpoints included the, individual responsiveness to inclisiran and the proportion of patients attaining global lipid targets for their level of ASCVD risk. The mean age at baseline was 55 years (range: 21 to 80 years), 22% were \geq 65 years old, 53% were women, 94% were White, 3% were Black, 3% were Asian and 3% were Hispanic or Latino

ethnicity. The mean baseline LDL-C was 4.0 mmol/l (153 mg/dl). Seventy-four percent (74%) were taking high-intensity statins, 15% were taking medium-intensity statins and 10% were not on a statin. Fifty-two percent (52%) of patients were treated with ezetimibe. The most commonly administered statins were atorvastatin and rosuvastatin.

Inclisiran significantly reduced the mean percentage change in LDL-C from baseline to day 510 compared to placebo by 48% (95% CI: -54%, -42%; p<0.0001). Inclisiran also significantly reduced the time-adjusted percentage change in LDL-C from baseline after day 90 and up to day 540 by 44% compared to placebo (95% CI: -48%, -40%; p<0.0001).

At day 510, 52.5% of inclisiran patients with ASCVD achieved their LDL-C target of <1.8 mmol/l (70 mg/dl) compared to 1.4% of placebo patients with ASCVD, while in the group with ASCVD risk equivalents 66.9% of inclisiran patients achieved their LDL-C target of <2.6 mmol/l (100 mg/dl) compared to 8.9% of placebo patients. Consistent and statistically significant (p<0.05) percentage change in LDL-C from baseline to day 510 and time-adjusted percentage change in LDL-C from baseline after day 90 and up to day 540 were observed across all subgroups irrespective of baseline demographics, baseline disease characteristics (including gender, age, body mass index, race and baseline statin use), comorbidities, and geographic regions.

1.1.5 Background to the research framework

There is evidence to show that real-world adherence with lipid lowering therapies is suboptimal (Akyea et al., 2019). The phase III clinical development programme summarised in Section 1.1.4 demonstrates the effective LDL-C reduction profile of inclisiran. In addition, the dosing regimen of 6-monthly maintenance injections provides a delivery method which may help to improve adherence to lipid lowering therapies with minimal impact on

The potential to address large population health burdens, such as cardiovascular disease, is greater in integrated healthcare systems that are able to support innovation. This requires understanding how a new technology such as inclisiran could be deployed and delivered into a system of care in such a manner that it would be possible to treat the appropriate patients at a population-health level.

The UK National Health Service (NHS) presents an ideal framework within which to consider population health approaches for the implementation of new health technologies. This is due to the primary care focused management of patients with chronic conditions, the increasing robustness of electronic medical records (EMR), clear and aligned commissioning processes and goals within the NHS Long-Term plan regarding the optimisation of service delivery to patients within their locality.

Within the NHS, the Greater Manchester Health and Social Care partnership - a geographical region covering in excess of 2 million patients – presents an ideal test-bed opportunity to research the implementation of inclisiran with a population health approach utilising a primary care model of delivery. This is due to the cohesion of the primary and secondary care EMR in Greater Manchester, their established use of implementation science approaches to assess new interventions and their established primary care networks.

The implementation research study described in this protocol is designed to provide and assess evidence for the implementation of inclisiran within a primary care setting in the NHS. The protocol describes an established implementation science approach utilising a Type 1 hybrid design described in subsequent sections.

2 Purpose and rationale

The purpose of this study is to evaluate the implementation of inclisiran in a regional primary care setting in the UK.

Using implementation science methodology, the study seeks to assess the effect of 9 months treatment with inclisiran +/- behavioural support, compared to standard of care + behavioural support, on LDL-C reduction, assessments of patient and healthcare professional (HCP) satisfaction, and healthcare service process evaluation.

3 Objectives

3.1 Primary Objective

The primary objective of this study is to demonstrate superiority of inclisiran +/- behavioural support compared to standard of care + behavioural support in a primary care setting, in terms of the percentage change in LDL-C from baseline to Day 270 in adults with elevated LDL-C.

3.2 Secondary Objectives

The secondary objectives of this study are to evaluate the implementation of inclisiran +/- behavioural support compared to standard of care + behavioural support in a primary care setting using the following assessments:

- Measures of patient satisfaction using the validated CSQ-8 (Client Satisfaction Questionnaire) administered after treatment at day 90.
- Measures of patient activation and empowerment using the validated Patient Activation Measure (PAM) questionnaire administered after treatment at day 90.
- Measures of adherence to cardiovascular disease self-management using the validated Patient Activation Measure (PAM) questionnaire administered after treatment at day 90 and using assessment of medication adherence during the study period.
- A process evaluation conducted using the Consolidated Framework for Implementation Research (CFIR) which will explore inclisiran delivery at three levels:
 - Feasibility and acceptability of delivery models for inclisiran to patients
 - Feasibility and acceptability of delivery models for inclisiran to providers (inner setting)
 - Wider 'transactability' of the proposed delivery models (outer setting)
 - The service costs of each delivery model
 - The acceptability and perceived sustainability of patient identification and referral routes

• Serious adverse event profile and adverse events leading to treatment discontinuation

4 Study design

This study is an implementation research study that utilises implementation science methodology and use of the electronic medical record (EMR).

The study is based on the following principles:

- It is run in the setting where inclisiran is intended to be implemented in clinical practice, with the intention of understanding the effects of innovations within the real world conditions of everyday clinical practice
- Inclusion / exclusion criteria reflect the proposed license, with the intention of working with populations that will be affected by an intervention, rather than selecting patients who are suitable for a standard clinical trial.
- Health delivery context: taking account institutional and health system contexts including the viewpoints of various stakeholder including commissioners, system managers and clinicians.

The primary focus of this study is implementation and 'transactability' – how to organise, deliver and maintain an innovative treatment for ASCVD in a primary care setting in a sustainable way.

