12.5 Analysis of secondary endpoints/estimands

12.5.1 Efficacy and/or Pharmacodynamic endpoint(s)

The following are key secondary efficacy endpoints:

- Mean difference in total score using the validated CSQ-8 (Client Satisfaction Questionnaire) administered after treatment at day 90.
- Mean difference in total score using the validated Patient Activation Measure (PAM) questionnaire administered after treatment at day 90.
- Measures of adherence to cardiovascular disease self-management using the validated Patient Activation Measure (PAM) questionnaire administered after treatment at day 90 and using assessment of medication adherence during the study period.
- A process evaluation conducted using the Consolidated Framework for Implementation Research (CFIR)

The analysis methodology used for the process evaluation is described separately in Section 4.3.

The key secondary endpoints will be analysed using an ANCOVA model that includes treatment and baseline value (as appropriate). Full details, including possible sensitivity analyses, will be provided in the SAP.

Descriptive summaries by treatment group will be presented.

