#### 2.5.2 Statistical hypothesis, model, and method of analysis

The primary effectiveness objective of this study is to demonstrate superiority of each inclisiran arm compared to control in terms of the percentage change from baseline in LDL-C to Day 270 in adults with elevated LDL-C. The statistical hypotheses that will be tested for each inclisiran arm are as follows:

- $H_0$ : The difference between participants treated with inclisiran and control in the least squares mean percentage change from baseline to the Day 270 visit in LDL-C= 0
- $H_a$ : The difference between participants treated with inclisiran and control in the least squares mean percentage change from baseline to the Day 270 visit in LDL-C < 0

The primary objective will be achieved if null hypothesis  $(H_0)$  rejected at the one-sided significance level of 0.025.

The primary analysis will use an analysis of covariance (ANCOVA) model on the percent change in LDL-C from baseline to Day 270 to test the superiority of inclisiran over control after missing data imputation.

Due to probable heterogeneity of variances between treatment groups, ANCOVA model which assumes unequal variances for treatment group will be used. The model will include the fixed effects of treatment group with baseline LDL-C as a covariate.

Multiple imputation will be used to impute missing data using a washout model specified in Appendix 5.5.1. A total of 500 imputed datasets will be created. The ANCOVA model will be fitted to each imputed dataset, and results will be combined using Rubin's combination rules. The estimate and corresponding 2-sided 95% confidence intervals of mean difference between treatment groups will be calculated. p-value for hypothesis test for mean difference will also be provided. The FAS will be used for this analysis. The family-wise error rate for comparisons of the two inclisiran arms with the lipid-lowering background therapy plus behavioural support arm will be controlled using the Holm procedure.

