#### 2.6.1.1 The CSQ-8 PROMs Questionnaire

The Client Satisfaction Questionnaire© (CSQ) is a portfolio of measurement instruments (CSQScales®) designed to assess consumer satisfaction with health and human services, including governmental and public benefit programs and services.

Each scale measures the recipients' direct satisfaction with specific services offered and received within a particular time frame from a specific provider or service setting.

The CSQ-8 has 8 items and no subscales. and It reports a single score measuring a single dimension of overall satisfaction.

A total score is produced by summing all item responses, with a higher scores indicating higher satisfaction. The outcome is the mean difference in total score between treatment groups. For the CSQ-8 version, scores range from 8 to 32, with higher values indicating higher satisfaction. Scoring for other versions is similar after extrapolating for number of items.

The following endpoint will be analyzed with CSQ-8 PROMs Questionnaire data.

**Endpoint:** Mean difference in total score using the validated CSQ-8 (Client Satisfaction Questionnaire) administered after treatment at day 90. **Summary measure:** Mean difference in total scores between treatment groups.

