#### 2.6.2 Statistical hypothesis, model, and method of analysis

The key secondary variables will be analyzed as follows:

- Mean difference in total score using the validated CSQ-8 (Client Satisfaction Questionnaire) administered after treatment at day 90 between the groups will be analyzed using ANOVA. The test statistics, mean difference, 95% confidence interval and the p-value obtained using the ANOVA will be presented.
- The comparison between inclisiran and inclisiran + behavioural support also will be done and presented as mentioned above. Inclisiran arm will be considered as control for this analysis.
- The descriptive statistics for the total CSQ score will be provided for each treatment group.
- Mean difference in total score using the validated Patient Activation Measure (PAM) questionnaire administered after treatment from baseline today 90 will be analyzed using ANCOVA model. ANCOVA model which assumes unequal variances for treatment group will be used. The model will include the fixed effects of treatment group with baseline total scores as a covariate. The estimate and corresponding 2-sided 95% confidence intervals of mean difference between treatment groups will be calculated. p-value for hypothesis test for mean difference will also be provided. The FAS will be used for this analysis.
- The comparison between inclisiran and inclisiran + behavioural support also will be done and presented as mentioned above. Inclisiran arm will be considered as control for this analysis.

| Novartis | Confidential | Page 22 of 37           |
|----------|--------------|-------------------------|
| SAP      |              | Study No. CKJX839A1GB01 |

• Measures of adherence to cardiovascular disease self-management using the validated Patient Activation Measure (PAM) questionnaire administered after treatment at day 90 and using assessment of medication adherence during the study period will be summarized by providing the frequency and percentages of subjects in the four levels of the PAM scores (below) by visit and treatment. Note, highly activated patients (level 3 and level 4) are more likely to adhere to cardiovascular self-management and thus medication adherence.

Level 1: Disengaged and overwhelmed

Level 2: Become aware but still struggling

Level 3: Taking action

Level 4: Maintaining behaviors and pushinng further

• Also frequency and percentage of subjects completed each item of PAM questionnaire will be summarized by visit and treatement.

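### CSQ-8 is compared by plain ANOVA, while PAM and LDL-C get arm-specific variances and no reason is given; its intervals could be modestly off if the spread differs by arm.

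*Protocol*

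**What the plan says.** The satisfaction objective is in Protocol 3.2: "Measures of patient satisfaction using the validated CSQ-8 (Client Satisfaction Questionnaire) administered after treatment at day 90". Protocol 12.5.1 and SAP 2.6.1 list CSQ-8 as a key secondary endpoint. Protocol 12.8 and SAP 3 say that CSQ-8 and PAM, not LDL-C, drive the sample size.

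The model is in SAP 2.6.2, where the CSQ-8 score "administered after treatment at day 90 between the groups will be analyzed using ANOVA". All inference comes from that fit: "The test statistics, mean difference, 95% confidence interval and the p-value obtained using the ANOVA will be presented". A third contrast is added: "The comparison between inclisiran and inclisiran + behavioural support also will be done and presented as mentioned above".

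For PAM, in the same list, the SAP says "ANCOVA model which assumes unequal variances for treatment group will be used". LDL-C is treated the same way in SAP 2.5.2, with a reason: "Due to probable heterogeneity of variances between treatment groups".

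Protocol 12.5.1 foresees ANCOVA with treatment and, where appropriate, baseline for the key secondary endpoints. It says nothing about variances. SAP 2.6.1.1 gives the CSQ-8 scale: "scores range from 8 to 32, with higher values indicating higher satisfaction". SAP 2.6.1 restricts these analyses to observed data.

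**The concern.** Where the SAP wants variances to differ by arm, it says so, and it does so twice. Plain ANOVA for CSQ-8 therefore reads as the usual model with one common residual variance. The absence of a baseline covariate would explain ANOVA instead of ANCOVA, but it does not explain a different variance assumption.

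A common variance may not hold for CSQ-8. The score is capped at 32, so an arm with higher satisfaction may be compressed at the top of the scale. The arms also rate different services: calls, an injection, or both.

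If three arms share one pooled variance, the third arm's spread enters the standard error of every pairwise comparison. The stated 95% coverage may then fail in either direction. The contrasts at stake are those with control and Group 3 v Group 2, which measures what behavioural support adds to inclisiran. No CSQ-8 sensitivity analysis is planned that would show the effect.

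**Working it through.** **1. The plan's own figure.** Inputs from Protocol 12.8: effect size 0.3, 90% power, one-sided 0.025, 20% drop-out.

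n per arm = 2 × (1.960 + 1.282)² / 0.3² = 233.5, so 234. Dividing by 0.8 gives 292.5, so 293. The planned 300 covers this. It leaves 300 × 0.8 = 240 evaluable per arm, with 90.8% power. The sample size reproduces and is not in question.

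**2. Formula for one three-arm ANOVA with equal numbers.** The ratio of the pooled standard error to the true one, for arms i and j, is

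r = √[ mean of the three variances / mean of the variances of i and j ].

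The actual two-sided error of a nominal 5% test is 2 × (1 − Φ(1.96 r)). If r is below 1 the interval is too narrow; if r is above 1 it is too wide.

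**3. Numbers.** Neither document gives a CSQ-8 SD, overall or by arm. The SDs below (Groups 1/2/3) are assumptions.

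| SDs | Contrast | r | Two-sided error |
|---|---|---|---|
| equal | any | 1 | 5.0% |
| 5/5/4 | 1 v 2 | √(22/25) = 0.938 | 6.6% |
| 5/5/3 | 1 v 2 | √(19.67/25) = 0.887 | 8.2% |
| 5/4/3 | 2 v 3 | √(16.67/12.5) = 1.155 | 2.4% |

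The only arm-specific SDs in the documents are for LDL-C: 30% and 20%, a ratio of 1.5. Applied to CSQ-8 purely as an illustration, with Group 1 the more variable arm, they give 6.7% for both contrasts with Group 1 and 2.0% for Group 2 v Group 3. A simulation (40,000 runs, 240 per arm) gives 6.7%, 6.9% and 1.9% with the pooled variance, and 4.9%, 5.2% and 5.0% with unequal variances.

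**4. Ceiling compression at about the planned effect.** Take latent normal scores with means 26, 26 and 27.5 and SD 5 in every arm, rounded and clipped to 8-32, with 240 per arm. The observed difference is 0.28 SD, close to the planned 0.3, and the observed SDs are 4.5, 4.5 and 4.2. For Group 1 v Group 2:

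r = √[ ((20.25 + 20.25 + 17.64)/3) / 20.25 ] = √(19.38/20.25) = 0.978, so the error is 5.5%.

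Repeated simulations of ceiling compression near the planned effect, including arms that start closer to the ceiling, mostly fall between 5.5% and 6.0% for this contrast. The other two contrasts fall slightly below 5%.

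**5. Separate two-arm ANOVAs.** With equal numbers the pooled and true standard errors agree, so the error is 5.0% at every SD ratio. With 200 v 260 forms and SDs 1.5 v 1 (the smaller arm more variable):

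- Pooled variance = (199 × 2.25 + 259 × 1)/458 = 1.543
- Pooled SE = √[1.543 × (1/200 + 1/260)] = 0.1168
- True SE = √(2.25/200 + 1/260) = 0.1229
- r = 0.951, so the error is 6.2%.

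**The case against.** The case against making much of this is substantial.

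- **The fault is conditional.** With equal variances the ANOVA is valid, and no CSQ-8 SD in the documents shows otherwise. This stands.
- **One three-arm fit is not stated.** SAP 2.6.2 describes Group 2 v Group 3 as an additional comparison with the inclisiran arm as its control, which fits separate two-arm analyses just as well. Under 1:1:1 allocation these stay near 5%. This also stands, with one limit: the questionnaires are posted back and only observed data are used, so returned numbers may differ by arm.
- **The larger errors need larger SD gaps.** Ceiling compression at about the planned effect moves the error by about one percentage point at most. Errors of 6.6-8.2% need gaps such as 5/5/4 or 5/5/3.
- **No confirmatory error rate is attached.** The Holm procedure covers only the two LDL-C comparisons, and CSQ-8 descriptive statistics by arm would let a reader see unequal spread. This limits the consequence. It does not explain the inconsistency.

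A reader might also infer that CSQ-8 is the endpoint for which equal variances are least plausible. The documents do not support that. PAM is bounded too (0 to 100), and LDL-C is the only endpoint with different SDs by arm and the only one for which the SAP calls heterogeneity probable.

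**Conclusion.** The point holds as an unexplained inconsistency with a modest, conditional effect. An endpoint that helps size the trial gets plain ANOVA, its neighbour in the same list gets arm-specific variances, and the SAP states neither a reason nor whether the CSQ-8 fit pools over three arms.

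On the assumption of one pooled three-arm fit, Group 1 v Group 2 has a two-sided error of about 5.5-6.0% at about the planned effect. For larger assumed SD gaps it is 6.6-8.2%, and a contrast between the less variable arms can fall to about 2%, with a loss of power. Which contrast is liberal depends on which arms vary more.

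A reader might go further and conclude that the CSQ-8 intervals and p-values are wrong in both directions. That does not follow: it needs both unequal variances and a three-arm pooled fit, and the documents establish neither. The change is still worth making, because it protects the error rate in every case considered and costs almost nothing.

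**What to change.** In SAP 2.6.2, analyse CSQ-8 with the same kind of unequal-variance linear model as PAM, without the baseline term: treatment group as fixed effect, arm-specific residual variances and Satterthwaite degrees of freedom. State that all three pairwise differences, their 95% intervals and p-values come from this one model. If plain ANOVA is kept, say whether it is fitted to three arms or to pairs, and why it differs from PAM.

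The cost is one SAP sentence and one program option. With 200 or more forms per arm the loss of degrees of freedom is negligible even if variances prove equal, and the sample size stays at 900. Fixing the model before the data are analysed also removes a later choice between two defensible CSQ-8 p-values.
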